incontinence; furthermore the pilot study was small, providing imprecise estimates. Thus, we conservatively assume a smaller net reduction in incontinence frequency of 6 episodes per week in the weight reduction compared to the control group, half the effect seen in the pilot study but large enough to be clinically meaningful. This corresponds to a standardized effect size of .43 SDs, assuming an SD of 14 episodes per week for the changes in frequency. We also assume that 10% of the sample will drop out before the 6-month visit; with imputation of baseline values for missing post-randomization incontinence frequencies, this attenuates the effect size in proportion to the dropout rate. Finally, we assume that clustering within the small intervention groups will induce a moderate design effect of 1.3. We adapted standard methods for two-sample comparisons of a continuous outcome to account for the design effect as well as the attenuation of the treatment effect size by imputation of baseline values. Under these assumptions, a sample of 330 women will provide at least 80% power in two sided tests with alpha of 5% to detect between-group differences of 6 incontinence episodes per week. Small to moderate gains in power may be obtained by the use of repeated measures, depending on the level of within-subject correlation.

12.2.2. Specific Aim #2. *To determine if randomization to a motivation-based maintenance program results in less weight regain from 6 to 18 months compared to a skill-based maintenance program.*

Analysis. Our hypothesis is that motivation-based weight maintenance will result in less weight regain than skill-based weight maintenance over the 12 months of the intervention. The predictor variable is random assignment to the motivation-based weight maintenance program compared to skill-based weight maintenance or control group, and the outcome is change in weight from the end of the weight reduction program at 6 months to the end of the maintenance period at 18 months. As in Specific Aim #1, we will use mixed linear regression models for change in weight over the maintenance period, controlling for group, degree of weight loss during the weight loss period, and taking account of clustering by weight loss group.

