Power estimates. Conservatively assuming a loss to follow-up of 15% between 6 and 18 months, the sample of 220 women randomized to motivation-based or skill-based maintenance strategies will provide 80% power to detect between-group differences in weight loss of 0.56 standard deviations. In prior TRIM

weight loss studies,⁷³ the standard deviation of weight loss at 18 months in the skill-based behavioral treatment condition was 6.8 kg, so that the minimum detectable between-group difference in average weight loss at the end of the study will be less than 3.8 kg.

12.2.3. Specific Aim #3. *To identify women who are most likely to experience improved continence after weight reduction, based on factors such as initial body mass index, body fat distribution and type of incontinence (stress, urge or mixed).*

Analysis. Our hypothesis is that some subgroups of women (defined by baseline body weight, body mass index, waist circumference, or type of incontinence), will be more likely to have improvement in incontinence with weight loss compared to others. Analyses in subgroups defined by these baseline variables will be similar to those described for Specific Aim #1. These subgroup analyses constitute comparisons between randomized groups, and are only mildly affected by the multiple comparisons problem. We will test for subgroup by treatment interactions.

Power estimates. Under the same assumptions used for Specific Aim 1, subgroups comprising 50, 40, or 30% of the sample will provide 80% power to detect standardized effects of approximately 0.58, 0.63, and 0.75 SDs, respectively, corresponding to changes of 8.5 to 10.5 episodes of incontinence per week.

12.2.4. Specific Aim #4 *To determine if randomization to a weight reduction program results in greater improvement in continence from baseline to 18 months compared to control and whether the motivation-based maintenance program results in greater improvements in continence than the skill-based maintenance program or control from baseline to 18 months.*

Analysis. Our hypotheses are that the weight reduction program will result in lower frequency of incontinence overall than in the control condition, and that motivation-based weight maintenance will result in lower frequency of incontinence than skill-based weight maintenance during the 18 months of follow-up. The predictor variables are random assignment to the weight

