12.3 Exploratory analysis of potential mechanisms for improvement in incontinence with weight loss. A series of closely related mixed linear models will be used to assess mechanisms by which the weight reduction intervention potentially affects measured incontinence frequency as well as related quality of life measures. We will first assess modification of the effects of treatment by baseline urodynamic measurements of leak point and intravesical pressures, to determine if the effectiveness of the weight reduction intervention varies by these parameters. To maximize efficiency, effect modification will be assessed as a continuous interaction between treatment assignment and the urodynamic measures. We will then examine the overall effects of assignment to the weight reduction group on the urodynamic measures as well as weight loss, to show the effect of the intervention on the proposed mediators. Next, we will use repeated measures models to determine the association between change since baseline in the proposed mediators and current incontinence frequency, to show that changes in the mediator are associated with changes in the primary outcome, and to determine which of the proposed mediators independently predict change in incontinence frequency. Finally, we will examine the attenuation of the estimated effect of treatment on incontinence frequency after controlling for changes in the proposed mediators, as an estimate of the proportion of the treatment effect explained. Confidence intervals for proportion of the treatment effect explained will be computed.⁷⁵

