2.0 CLINICAL TRIAL OBJECTIVES

The primary aims of PRIDE are:

1. to determine whether randomization to a weight reduction program results in greater reductions in frequency of incontinence episodes at 6 months compared to control;
2. to identify women who are most likely to experience improved continence after weight reduction, based on factors such as initial body mass index, body fat distribution and type of incontinence (stress, urge or mixed).

As a part of PRIDE we plan to:

1. conduct exploratory analyses to evaluate whether baseline urodynamic measures can identify women who are most likely to experience improved continence after weight reduction and;
2. investigate the mechanism by which weight loss improves continence by examining the relationship of improvement in continence and changes in urodynamic measures.

CONFIDENTIAL

To achieve these aims, the pelvic floor evaluation and urodynamic testing (UDS) will be performed on the first 50 volunteers at each site who agree and sign a separate informed consent. Standardized urodynamic testing will take place at baseline and again at the 6-month follow-up study visit.

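### Aim 3 gives power only for effects inside single subgroups, not for its planned interaction test (80% power needs differences of about 10 to 13 episodes/week), and calls multiplicity mild on a ground that does not support it

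*Protocol*

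**What the plan says.** Protocol section 12.2.3 (Specific Aim #3) sets out to find which women are most likely to improve. Its hypothesis is that some subgroups, defined by baseline body weight, body mass index, waist circumference or type of incontinence, will improve more than others. It plans two kinds of analysis: Aim 1-type comparisons inside subgroups, and tests of subgroup-by-treatment interaction.

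On multiplicity it says: "These subgroup analyses constitute comparisons between randomized groups, and are only mildly affected by the multiple comparisons problem".

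On power it says, "Under the same assumptions used for Specific Aim 1", that "subgroups comprising 50, 40, or 30% of the sample will provide 80% power to detect standardized effects of approximately 0.58, 0.63, and 0.75 SDs", "corresponding to changes of 8.5 to 10.5 episodes of incontinence per week". It gives no power or detectable difference for the interaction tests.

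Two other places bear on this. Section 12.3 says of the urodynamic substudy that "effect modification will be assessed as a continuous interaction between treatment assignment and the urodynamic measures", and gives efficiency as the reason. The main protocol (section 3.2) lists Aim 3 as secondary, while the urodynamic protocol (section 2.0) puts the same question, "to identify women who are most likely to experience improved continence after weight reduction", among the primary aims of PRIDE.

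**The concern.** Whether one group of women benefits more than another is a question about the difference between two treatment effects. A well-powered effect in heavier women does not show that heavier women gain more than lighter women; the interaction test does. The only power in the section belongs to the other analysis, so a reader has no warning of how weak the interaction test is.

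The multiplicity sentence compounds this. Its only support is that the comparisons are between randomized groups. Randomization within a subgroup protects against confounding, but it does nothing about the error that accumulates when several factors are each tested at 5%.

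At stake is how the Aim 3 results are read. A finding that is significant in one subgroup and not in its complement could be taken as identifying responders, with the protocol cited for adequate power and little false-positive risk.

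**Working it through.** **Inputs.** From the Aim 1 sample size text (12.2.1), which Aim 3 adopts: 330 women, two-sided alpha 5%, power 80%, SD of change 14 episodes/week, overall effect 6 episodes/week, 10% dropout with baseline imputation (true effect multiplied by 0.9), design effect 1.3. From 8.2.1: 2:1 allocation, hence 220 and 110. The normal approximation is used throughout; 1.960 + 0.842 = 2.8016 before rounding.

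**Aim 1 check.** Standard error of the difference in SD units: √(1.3/220 + 1.3/110) = 0.1331. Attenuated effect: 6 × 0.9/14 = 0.3857. Power = Φ(0.3857/0.1331 − 1.96) = 82.6%, which agrees with the protocol's "a sample of 330 women will provide at least 80% power". Full-sample detectable effect: 2.8016 × 0.1331/0.9 = 0.4145 SD.

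**Reproducing the Aim 3 figures.** Inside a subgroup of fraction f the detectable effect is 0.4145/√f:

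| f | Stated SD | Recomputed SD | Recomputed episodes | Power at stated SD |
|---|---|---|---|---|
| 50% | 0.58 | 0.586 | 8.2 | 79.2% |
| 40% | 0.63 | 0.655 | 9.2 | 76.8% |
| 30% | 0.75 | 0.757 | 10.6 | 79.3% |

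The stated figures are therefore single-subgroup effects. The 50% and 30% figures reproduce; the 40% figure falls about three points short of 80% power if 1.3 is kept.

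**Episode range.** 0.58 × 14 = 8.1, not 8.5. The upper end is right: 0.75 × 14 = 10.5.

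**Interaction.** For complementary subgroups f and 1 − f with equal SD, the detectable difference between the two treatment effects is 0.4145 × √(1/f + 1/(1 − f)). If both subgroups sit in the same counseling groups and the shared group effect cancels, divide by √1.3.

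| Split | Multiplier | With 1.3 | If clustering cancels |
|---|---|---|---|
| 50/50 | 2.000 | 0.829 SD = 11.6 episodes | 0.727 SD = 10.2 |
| 40/60 | 2.041 | 0.846 SD = 11.8 | 0.742 SD = 10.4 |
| 30/70 | 2.182 | 0.904 SD = 12.7 | 0.793 SD = 11.1 |

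**Power for given interactions.** Power = Φ(2.8016 × d/d80 − 1.96), where d80 is the detectable interaction in the table.

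- For 6 episodes (6/14 = 0.429 SD), the lowest value is 30/70 with 1.3: Φ(2.8016 × 0.429/0.904 − 1.96) = 26%. The highest is 50/50 with clustering cancelled: Φ(2.8016 × 0.429/0.727 − 1.96) = 38%.
- For 0.58 SD, the 50/50 split gives 50% with 1.3 and 61% with clustering cancelled. The 30/70 split gives 44% and 54%. The range over all three splits is 44 to 61%.

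**Multiplicity.** Four independent tests at 5%: 1 − 0.95⁴ = 18.5%. Weight, BMI and waist overlap, so the actual figure lies below this and above 5%. The protocol gives no correlations from which to narrow it.

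**The case against.** The strongest reply is that the power sentence is not wrong. The section plans within-subgroup analyses, the sentence speaks of subgroups of a given size, and nowhere does it claim 80% power for an interaction. This stands. A reader might infer that the protocol misstates the power of its test; the text supports only that power is given for one of two planned analyses, and not for the one that answers the comparative question.

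The 0.63 figure can also be defended. If the design effect shrinks because each counseling group contributes only 40% of its members, then with groups of 14 (DSMB guidelines, Appendix III) and the intraclass correlation implied by 1.3 (assumed: 0.3/13 = 0.023), the subgroup design effect is 1 + (0.4 × 14 − 1) × 0.023 ≈ 1.11. The detectable effect is then 0.60 SD, and 0.63 is conservative. So 0.63 falls short only if 1.3 is kept, and the text says the figures are approximate. The 8.5 slip also errs on the cautious side.

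A reader might take 18.5% as the false-positive rate. It is the ceiling under independence, which three overlapping measures of body size will not meet.

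It may be said that interaction power and multiplicity adjustment belong in an analysis plan that is not shown. That would excuse silence. It does not excuse a statement that multiplicity is mild for a reason that does not bear on it. Committing to interaction tests is a real safeguard against misreading subgroup results, but it does not supply their missing power.

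**Conclusion.** The point holds as a should-fix. The stated 0.58, 0.63 and 0.75 SD are approximately right for effects inside one subgroup, with about 77% power for the 40% subgroup if the design effect of 1.3 is retained. They say nothing about the interaction test, whose 80%-power difference is 11.6 to 12.7 episodes/week, or 10.2 to 11.1 if clustering cancels. Even an interaction as large as the full assumed effect of 6 would be missed more often than found.

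These figures rest on the Aim 1 assumptions, two complementary subgroups and equal SDs. A continuous interaction could do better, and three incontinence types would do worse. The multiplicity sentence is wrong in its reasoning, whatever the exact inflation, and 8.5 should be 8.1.

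A reader might rank this higher because the urodynamic protocol lists the question as primary. The main protocol lists it as secondary, and the urodynamic protocol refers to the main protocol for the full study description. The labels should be reconciled, but the mismatch does not make this a defect in the trial's primary analysis.

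**What to change.** In section 12.2.3:

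1. Label the existing figures as power for a treatment effect within one subgroup, and start the episode range at 8.1. For the 40% subgroup, either state 0.655 SD or say which design effect was used.
2. Add the detectable interactions: 0.83, 0.85 and 0.90 SD (11.6, 11.8, 12.7 episodes/week) for 50/50, 40/60 and 30/70 splits, with 10.2 to 11.1 episodes if clustering cancels. Say that they apply to two-level splits.
3. Delete the sentence calling multiplicity mild.
4. State that any claim of differential benefit rests on the interaction tests, with a multiplicity adjustment such as Holm over the named factors.
5. Test body weight, BMI and waist as continuous interactions, as section 12.3 already does for the urodynamic measures. Note that the two-level figures are only a guide for these tests and for a three-level incontinence type.

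The cost is protocol wording and a less favourable statement of power. No extra participants or data are needed.

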8.2 Randomization Procedures

8.2.1 Randomization to Weight Loss or Control. Women will be randomly allocated in a 2-to-1 ratio to either the weight reduction program or control condition. Randomization will be stratified by clinical center. Blocked randomization within each of the centers will then be performed to ensure that the number of participants in the two treatment groups is close to our goal of an exact 2 to 1 ratio. Since the intervention is not strictly blinded, block size will vary randomly from 3 to 6 in a schedule that is not known to investigators. In addition, to assure an even distribution of treatment groups, a separate set of randomization envelopes will be prepared, as described above, for women who choose to have the urodynamic assessment. Thus, the randomization will be stratified both by center and whether or not the participant volunteers for the urodynamic assessment.

Using computer algorithms for a 2 to 1 randomization, Coordinating Center staff will prepare two sets of sealed, opaque envelopes for each clinical center, color coded for urodynamic assessment or no urodynamic assessment. On the outside, the envelopes will be numbered consecutively with the randomization sequence number; on the inside the envelopes will contain study group assignment. When eligibility has been confirmed by completion of the eligibility checklist, clinical center staff will enter the date, participant's name, and study ID (assigned at the screening visit) consecutively in a randomization log, select the next numbered randomization envelope from the appropriate color-coded series, enter the randomization sequence number listed on the outside of the envelope, then open the envelope and enter the study group assignment contained inside the envelope on the randomization log. All opened and unopened envelopes will be retained at the clinical center for review during study site visits and at the end of the trial. Randomization dates and times should follow the order of the randomization sequence numbers, providing a check on validity. Screening data

will be retained by study ID for women not randomized, facilitating review of the recruitment process.

Participants will be randomized in “waves” of about 30 – 40 at a time to accommodate the formation of intervention or control groups. Eligibility is determined during screening visits.

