8.4.11. Quality-of-life Measurements

Incontinence Impact Questionnaire. The Incontinence Impact Questionnaire is a validated instrument that measures the impact of incontinence on social

activity, physical activity, travel, and emotional health on a 4-point Likert scale, with the sum of responses transformed into a score on a 0-100 continuous scale.

Urogenital Distress Inventory. The Urogenital Distress Inventory is a validated instrument that has been used extensively in incontinent populations to quantify incontinence symptom bothersomeness.⁵⁹ The degree of bothersomeness of irritative, obstructive/discomfort, and stress symptoms is recorded on a 4-point Likert scale with the sum of responses transformed into a score on a 0-100 continuous scale.

Short Form 36. The Short Form 36 is a 36-item measure that was drawn from the 149-item full set of the Medical Outcomes Study (MOS) Functioning and Well-Being Profile.^{60, 61} Two summary scales can be calculated, the physical component summary and the mental component summary.⁶¹ The physical component summary subscale addresses the areas of greatest importance to women with both incontinence and overweight and obesity. Large differences in change scores on this subscale have been observed when overweight and obese women reduce weight^{62, 63} and with improvement in incontinence severity.

Participant satisfaction with health. We will include a rating of satisfaction with changes in incontinence used in prior incontinence treatment studies.^{35, 36} This is a self-report ordinal scale and measures how participants feel about their treatment outcomes.

Beck Depression Inventory. The Beck Depression Inventory ⁶⁴ is a 21-item self-reported measure of depressive symptoms. It will be used in our study to assess changes in depressive symptoms related to randomization to the weight loss intervention, to the motivation-based weight maintenance program, and to changes in weight and frequency of incontinence.

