reduction program or to the motivation-based weight maintenance program compared to skill-based weight maintenance, or to the control group, and the outcome is change from baseline to the end of the weight loss intervention at 18 months in frequency of incontinence episodes. Analyses will be similar to those described above for specific aim 1.

12.2.5. Specific Aim #5. *To determine if randomization to a weight reduction program results in greater improvement in quality of life from baseline to 6 and 18 months compared to the control condition.*

Analysis. Our hypothesis is that randomization to a weight reduction program will result in greater improvements in quality of life measures than to a control condition at both 6 and 18 months of follow-up. The predictor variable is assignment to the weight reduction or control groups and the outcome is change in quality of life outcomes including Incontinence Impact Question (IIQ), Urogenital Distress Inventory (UDI) and Short Form-36 (SF36), from baseline to 6 and 18 months. Analyses will be similar to those described above for specific aim 1. In addition to the primary analysis comparing weight reduction to a control condition, we will also make pairwise comparisons between motivation-based maintenance, skill-based maintenance, and the control condition at 18 months.

Power estimates. Under the assumptions used for Specific Aims 1 and 2, the sample of 330 women will provide 80% power to detect actual treatment differences of 0.43 SDs in the primary comparison between weight loss and control at 6 months, and 0.49 SDs at 18 months. In pairwise comparisons between the three groups at 18 months, we will be able to detect differences of 0.56 SDs. These are small to moderate differences, as shown below.

Instrument	SD of single measures	Minimum detectable difference in changes**
UDI	50 ⁵⁹	22-28
IIQ	60 ⁵⁹	26-34
SF36 PCS*	25-30 ⁶³	16-18
BDI	4.5 ⁷⁴	19-25

* Physical component scale

** Assuming within-subject correlation of repeated measures of 0.5

In all cases, smaller between group differences in change would be detectable if within-subject correlation exceeds 0.5.

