10.4.2.4 Beck Depression Inventory (4 pages)

This questionnaire should be completed by the participant during the clinic visit and should be reviewed by a PRIDE staff member before the participant goes home.

Only one bubble should be selected for each question. There are 21 questions (A to U), with four possible responses to each question, listed in the order of feeling best to feeling worst. Responses are scored on a scale of 0 – 3, with 0 being the first listed response (not depressed) and 3 being the last listed response (most depressed). The questionnaire should be reviewed during the clinic visit while the participant is otherwise occupied.

A participant with a total depression score ≥ 24 on the BECK INVENTORY may be depressed, and careful consideration should be given as to whether participation in PRIDE is appropriate for her. The participant should be told she might be depressed, and referred to her health care provider for evaluation. If the response to question “I” on the BECK INVENTORY, about suicide intent, is the third or fourth response listed, (i.e. “I would like to kill myself” or “I would kill myself if I had the chance”) she should be evaluated immediately by a qualified psychiatric clinician.

If it is felt that this woman is not an appropriate candidate for PRIDE, update the Inclusion/Exclusion checklist by marking “Yes” for Exclusion Criteria I.

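### In the Aim 5 table, the BDI and SF-36 PCS detectable differences do not follow from the protocol's own rule, and the IIQ and UDI SDs contradict the stated 0-100 scale

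*Protocol*

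**What the plan says.** Section 12.2.5 (Specific Aim #5, Power estimates) says that "the sample of 330 women will provide 80% power to detect actual treatment differences of 0.43 SDs" in the 6-month comparison of weight loss with control. It adds 0.49 SDs for the same comparison at 18 months and 0.56 SDs for pairwise comparisons of the three groups at 18 months. It then remarks "These are small to moderate differences, as shown below" and tabulates, for each instrument, the SD of a single measure and the minimum detectable difference in changes:

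| Instrument | SD | Detectable difference |
|---|---|---|
| UDI | 50 | 22-28 |
| IIQ | 60 | 26-34 |
| SF-36 PCS | 25-30 | 16-18 |
| BDI | 4.5 | 19-25 |

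The footnote to the last column reads "Assuming within-subject correlation of repeated measures of 0.5". The initial protocol and the text under Amendment #5 carry the same rows.

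Section 8.4.11 describes IIQ and UDI in the same way, each "with the sum of responses transformed into a score on a 0-100 continuous scale". For the BDI, section 10.4.2.4 of the operations manual says "There are 21 questions (A to U), with four possible responses to each question", scored 0 to 3.

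**The concern.** The table converts three standardized effects into points on four instruments. Two rows follow one simple rule and two do not. The BDI row is the most visible: a difference of 19-25 points is more than four SDs of the instrument and cannot be described as small to moderate. For IIQ and UDI the multiplication is right, but the SDs do not fit the scale on which the protocol says the scores will be expressed.

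What is at stake is interpretation. The table is where a reader finds, in instrument points, how large a quality-of-life difference the trial was planned to detect, for example when judging whether a null result is informative. As printed, no row can be used for that purpose without correction or a clear scoring range.

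**Working it through.** **Inputs.** N = 330, allocated 2:1 (section 8.2.1: "Women will be randomly allocated in a 2-to-1 ratio to either the weight reduction program or control condition"), so 220 and 110. Two-sided 5% test and 80% power (section 12.2.1). Design effect 1.3 (section 12.2.1: "clustering within the small intervention groups will induce a moderate design effect of 1.3"). 10% dropout by 6 months, which attenuates the effect (section 12.2.1). A further 15% loss from 6 to 18 months (section 12.2.2). Within-subject correlation 0.5 (table footnote).

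**Step 1: do the standardized effects hold?** Detectable effect = (1.960 + 0.842) × √[1.3 × (1/n1 + 1/n2)] / fraction retained.

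- 6 months, 220 v 110: 0.373 / 0.90 = 0.414. The stated 0.43 has 82.8% power, so it is slightly conservative.
- 18 months, 220 v 110: 0.373 / (0.90 × 0.85) = 0.488. The stated 0.49 has 80.4% power.
- 18 months, pairwise, 110 v 110: 0.431 / (0.90 × 0.85) = 0.563. The stated 0.56 has 79.6% power.

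All three are supported.

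**Step 2: the conversion rule.** SD of change = SD × √[2(1 − 0.5)] = SD. Each row should therefore run from 0.43 × SD to 0.56 × SD.

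| Instrument | SD | 0.43 × SD | 0.56 × SD | Printed |
|---|---|---|---|---|
| UDI | 50 | 21.5 | 28.0 | 22-28, agrees |
| IIQ | 60 | 25.8 | 33.6 | 26-34, agrees |
| SF-36 PCS | 25 to 30 | 10.75 (SD 25) | 16.8 (SD 30) | 16-18, does not agree |
| BDI | 4.5 | 1.94 | 2.52 | 19-25, does not agree |

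**BDI.** 19/1.94 = 9.8 and 25/2.52 = 9.9, which is a factor of ten after rounding. The printed range is 19/4.5 = 4.2 to 25/4.5 = 5.6 SDs. Under the rule it would need an SD of about 44 (19/0.43 = 44.2; 25/0.56 = 44.6). With 21 items scored 0 to 3 the total runs from 0 to 63, and the largest possible SD is 63/2 = 31.5.

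**SF-36 PCS.** The printed ends need multipliers of 16/25 = 0.64 and 18/30 = 0.60. Both exceed the largest stated multiplier, 0.56. Changing the correlation does not help: the lower end would need a correlation of about −0.11 and the upper end about 0.43. A different SD alone would not give 16-18 over the same span either. The rule fixes the ratio of upper to lower end at 0.56/0.43 = 1.30 or more, whereas 16-18, allowing for rounding, has a ratio of at most 18.5/15.5 = 1.19.

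**IIQ and UDI.** For a score confined to [0, 100], the largest SD is (100 − 0)/2 = 50, reached only when half the women score 0 and half score 100. An IIQ SD of 60 is above this. On a 0-100 scale the IIQ detectable difference could be at most 0.43 × 50 = 21.5 to 0.56 × 50 = 28.0, against the printed 26-34. A UDI SD of 50 lies exactly at the limit.

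**The case against.** The strongest reply is that nothing in the design depends on this table. N = 330 rests on Aim 1. The correct standardized effects stand directly above the table. No analysis model, test or stopping rule uses the point values. Taking the stated SDs as given, the errors make the detectable difference look larger than it is, so no power is falsely claimed. Amendment #5 is dated May 2007, after the planned end of recruitment in October 2006, so a corrected table changes no design decision. All of this stands and limits the weight of the point.

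It may also be said that 19-25 is 1.9-2.5 with the decimal points lost, perhaps only when the PDF was read. That cannot be excluded entirely. It is unlikely, because 4.5 in the same row keeps its decimal and both protocol texts show 19-25. It could not explain the PCS row in any case. BDI is also not among the outcomes named in the Aim 5 analysis text, although the power table and section 8.4.11 include it.

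A reader might infer more than the documents support:

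- That the detectable effect for Aim 5 is unknown, or that the trial cannot see any plausible change in mood. The SD-based figures are stated and reproduce; for BDI they mean about 2 points.
- That the IIQ and UDI SDs come from a different scoring range. This is a possible explanation, but the protocol shows only the contradiction. Either the SDs or the description of the scale could be at fault, and the source cited for the SDs is not available here.
- That 11-17 is certainly the right PCS range. It is right if the SD of 25-30 is right, which the protocol does not settle.
- That every row is miscalculated. The UDI and IIQ multiplications are correct. The UDI SD is implausible on 0-100 but not strictly impossible.

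**Conclusion.** The point holds as a documentation error in the power section for a secondary aim. Two of the four rows do not follow from the protocol's own multipliers and correlation: BDI is overstated tenfold (19-25 against 1.9-2.5), and SF-36 PCS is printed as 16-18 against 10.8-16.8, with the larger gap at the lower end. The other two rows are arithmetically right but rest on SDs that contradict the 0-100 scale: impossible for IIQ (60 against a maximum of 50) and at the theoretical limit for UDI.

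The standardized effects of 0.43, 0.49 and 0.56 SD and the sample size are unaffected. The description of the differences as small to moderate fits those effects but not the BDI row as printed.

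The recomputed BDI and PCS ranges assume that the stated SDs are correct, that the correlation is 0.5 as in the footnote, and that these rows are meant to span the same comparisons as the UDI and IIQ rows.

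**What to change.** In the section 12.2.5 table:

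1. Restate BDI as 1.9-2.5.
2. Check the SF-36 PCS SD against its source. If 25-30 is right, restate the range as about 11-17. If the SD is the wrong entry, correct it and recompute the range as 0.43 to 0.56 times the corrected SD.
3. For IIQ and UDI, state one scoring range, use it in both section 8.4.11 and the table, give SDs on that range, and recompute as 0.43 to 0.56 times SD.

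The cost is a corrected table and a sentence on scoring. If reconciling the scale means changing how IIQ or UDI will be scored, rather than only correcting the SDs, that is a change to the outcome definition and should be recorded as such before the scores are analyzed. The sample size and analysis models do not change.
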